8.2. Right Heart Catheterization and Implant Procedure (Baseline Visit)

Before the RHC, the following procedures/assessments will be performed:

- Abbreviated physical examination (i.e., vital sign assessments and significant changes since Screening Visit) and weight
- Confirmation of enrollment eligibility (other than angiographic criteria)
- PT/PTT with International Normalized Ratio (INR) of 1.5 or less for subjects previously on warfarin
- Assessment of heart failure medications
- Record any medical history updates since screening visit.

This confidential document is the property of Abbott and shall not be reproduced, distributed, disclosed or used without the express written consent of Abbott

Clinical Investigation Plan

The patient will then undergo a standard RHC. A selective, hand injected pulmonary angiogram will be performed via the pulmonary artery catheter to identify a suitable pulmonary artery branch for sensor implantation. Subjects must have an appropriately sized ($\geq 7\text{mm}$ diameter) pulmonary artery branch. Subjects who do not meet this inclusion criteria will not receive the PA Sensor implant and will be considered ineligible for the study. These subjects will be documented as consented not implanted and will be followed for 30 days for safety. Patients with a suitable target pulmonary artery branch will undergo:

- Wireless implantable hemodynamic sensor implant
- Pulmonary artery catheter measurements (pulmonary systolic, pulmonary diastolic, pulmonary mean, cardiac output) done 3 times consecutively with sensor measurements for setting of sensor baseline.
- Provide post-procedure vascular access site care per standard procedure
- At the Investigator's discretion, subjects should be discharged once stable with respect to the procedure and their heart failure.
- Please see User's Manual for implant details

Subjects who are currently on anticoagulant therapy (warfarin, or any FDA approved anticoagulant) will restart treatment. The subject's INR should be checked periodically to ensure that it is in the therapeutic range. Those subjects not on chronic warfarin will be placed on anticoagulant/antiplatelet therapy as indicated in the device User's Manual. Refer to the User's Manual for further details.

8.3. Study Follow-Up Visits 1, 2, 3, 4, and 5 (Months 1, 6, 12, 18, and 24)

Implanted subjects will be evaluated at Month 1 (± 7 days) and at Months 6, 12, 18, and 24 (± 30 days) and the following procedures/assessments will be performed:

- Updated medical and surgical history
- Assessment of AEs that occurred since the last visit
- Abbreviated physical examination (significant changes since previous visit) including vital signs (heart rate, respiratory rate, blood pressure), and weight
- Assessment of NYHA functional class
- Kansas City Cardiomyopathy Questionnaire (KCCQ-12)
- Brief Illness Perception Questionnaire
- Cardiac Health Security Survey
- Heart failure medication review
- PA pressure measurements may be obtained at the Investigator's discretion

This confidential document is the property of Abbott and shall not be reproduced, distributed, disclosed or used without the express written consent of Abbott

Clinical Investigation Plan

Subjects will be reminded to obtain pulmonary artery pressure measurements utilizing the CardioMEMS HF System as directed. Subjects will be reminded of the current ACC/AHA guidelines regarding sodium and fluid restrictions.

The study coordinator or designee will administer patient-reported outcome questionnaires. It is important that the subject understands the meaning of all words and instructions in each questionnaire and answers all the questions. The subject will be instructed to ask any questions about the questionnaire if further explanation is needed. The research coordinator or designee will review the questionnaires to verify that all questions have been answered. The Patient Reported Outcomes will be obtained at 6, 12, 18 and 24 months. Patients who were enrolled in the study prior to addition of patient reported outcome questionnaires, and therefore did not complete baseline questionnaires, are not required to complete questionnaires at the follow-up visits.

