9.1.2. Sensor Failure Criteria

A Sensor failure occurs when no readings can be obtained from it after troubleshooting the system to rule out any problems with the external electronics.

EFFECTIVENESS ANALYSES

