12.2. Sample Size Considerations

Effectiveness Sample Size Determination

For the primary effectiveness endpoint of HF hospitalization rate during 1 year, 300 patients will provide greater than 90% power to meet the efficacy goal (upper confidence limit less than the HF hospitalization rate in the year prior to enrollment), using a one-sample, two-sided Poisson confidence interval with alpha of 0.05.

Safety Sample Size Determinations

For the two-year primary safety endpoint of freedom from device-related complications, using an exact two-sided test for one-sample binomial proportions with alpha of 0.05, a sample size of 619 subjects will provide greater than 90% power to detect a difference as small as 5% from the null proportion rate of 0.80 (i.e., objective performance criterion of 80%). For sensor failures at 2 years, a sample size of 663 subjects provides greater than 90% power to detect a difference as small as 3.5% from the null proportion rate of 0.90 (i.e., objective performance criterion of 90%).

This confidential document is the property of Abbott and shall not be reproduced, distributed, disclosed or used without the express written consent of Abbott

Clinical Investigation Plan

Thus, the sample size for this study is driven by the safety endpoints. The 2 year attrition rate in CHAMPION was 49.1% (228/550). To ensure sufficient patients are enrolled to adequately evaluate safety and efficacy, 1200 subjects will be enrolled.

Note that at least 35% of the 1200 enrolled patients (420) must be women resulting in approximately 206 women completing the trial (assuming a 49% attrition rate). This sample size will provide greater than 90% power to meet the goal for effectiveness. Regarding freedom from device-related complications and freedom from sensor failures, 206 women will provide greater than 90% power to detect a difference as small as 0.06 from the null proportion rate of 0.90.

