12.6.1. Primary Safety Endpoints

The primary safety analyses will be based on the following objective performance criteria: a) the lower limit of the two-sided 95% confidence interval on the freedom from device / system-related complication rate at 24 months is greater than 80% and b) the lower limit of the two-sided 95% confidence interval on the freedom from pressure sensor failure rate at 24 months is greater than 90%. These primary safety endpoints will be tested hierarchically in order to control for multiplicity. First, the freedom from device / system-related complication rate will be tested. If the result is statistically significant (i.e., $p < 0.050$), then the freedom from pressure sensor failure rate will also be tested for significance (i.e., $p < 0.050$). The study will be judged to have provided positive safety results if both tests of the primary safety analysis endpoints are statistically significant (i.e., $p < 0.050$).

Mathematically stated, the primary safety hypotheses are:

a) $H_0: P_{(\text{Freedom from device / system-related complications at 24 months})} \leq 80\%}$

$H_a: P_{(\text{Freedom from device / system-related complications at 24 months})} > 80\%$

b) $H_0: P_{(\text{Freedom from pressure sensor failure at 24 months})} \leq 90\%$

$H_a: P_{(\text{Freedom from pressure sensor failure at 24 months})} > 90\%$

Plotting and analysis of safety endpoints will also be displayed using Kaplan-Meier methods.

This confidential document is the property of Abbott and shall not be reproduced, distributed, disclosed or used without the express written consent of Abbott

Clinical Investigation Plan

Safety will also be assessed throughout the study by the frequency of Adverse Events (AEs), Adverse Device Effects (ADEs), Serious AEs (SAEs), and Serious Adverse Device Effects (SADEs), and device / system-related complications by relationship to the device via Medical Dictionary for Regulatory Activities (MedDRA) system organ classification. Physical examination, and subject survival data through 24 months will be tabulated across study period assessments.

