APPENDIX B: Schedule of Events

	Screening	Baseline (Implant)	Month 1	Months 6 and every 6 Months thereafter until Study Termination
Procedures		(within 30 days of Screening)	Visit 1 (30 ± 7 days)	Visits 2-5 or Study Termination (± 30 day window)
Informed Consent	X			
Demographics	X			
Past Medical & Surgical History	X			
Inclusion/Exclusion Criteria Review	X	X		
GFR	X			
Kansas City Cardiomyopathy Questionnaire (KCCQ-12)	X			X
Brief Illness Perception Questionnaire	X			X
Cardiac Health Security Survey	X			X
INR (if indicated)		X		
Pulmonary artery measurement		X		
Physical Examination (including weight)	X ¹	X ²	X ²	X ²
NYHA HF Classification	X		X	X
Pulmonary Artery Angiography		X		
Sensor Implant		X		
Sensor Measurements		X	X (Investigator discretion)	X (Investigator discretion)
Adverse Events Assessment		X	X	X
Medication Assessment (heart failure)	X	X	X	X

¹ Includes weight, height and vital signs (temperature, blood pressure, pulse, respirations).

² Includes weight, vital signs and significant changes from previous physical examination

Clinical Investigation Plan

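### Sensor failure at 24 months can be found only by attempting a reading, yet no follow-up or exit visit requires one, and the plan does not classify a sensor with no recent reading

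*Combined protocol and SAP*

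**What the plan says.** Section 12.6.1 sets the criterion: "the lower limit of the two-sided 95% confidence interval on the freedom from pressure sensor failure rate at 24 months is greater than 90" per cent. Both primary safety tests must succeed for a positive safety result, and the sub-study repeats the endpoint (13.9.1).

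Section 9.1.2 defines the event: "A Sensor failure occurs when no readings can be obtained from it after troubleshooting the system" to exclude a fault in the external electronics. Without an attempted reading, no failure can be declared.

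After implant, no study visit requires that attempt:
- Section 8.3, Months 1, 6, 12, 18 and 24: "PA pressure measurements may be obtained at the" investigator's discretion.
- Section 8.6, early exit: a reading is again optional.
- Appendix B, sensor measurements at Month 1 and at Visits 2 to 5 or study termination: "X (Investigator discretion").
- Section 8.5: hospital, emergency room and clinic readings are discretionary. A comparative reading is expected only if a right heart catheterization is clinically warranted.

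The implant visit does require sensor measurements (8.2). Between visits, home readings are daily or as the physician directs, the sponsor tracks compliance and reports it to the investigator, and the investigator reviews readings at least weekly (Study Design).

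None of sections 9.1.2, 12.3 and 12.6.1 says how to classify a sensor whose status at 24 months is unknown. Unresolved missing data are not imputed (12.3), and Kaplan-Meier is an additional display with no stated censoring rule (12.6.1).

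**The concern.** The endpoint asks whether the sensor still works at two years, but the plan observes this only in patients who keep using it. Suppose a patient stops reading at Month 8 and attends Month 24, where the investigator takes no reading. The last evidence that the sensor worked is then 16 months old. If it failed in between, no failure need ever be recorded.

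The plan foresees lapses in use. Compliance is a reported outcome (12.7.2), and the Cardiac Health Security Survey has an item on losing interest in monitoring (Appendix G). The surrounding processes would show that readings have stopped, but none converts non-use into a test of the sensor. The 7-day reminder in the Study Design section is triggered by missing site logins, not by missing patient readings.

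At stake is one of the two tests that decide the primary safety conclusion. If an undetected failure is counted as failure-free, the error can run in only one direction, towards passing.

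**Working it through.** **Inputs from the plan.** The method is described as "using an exact two-sided test for one-sample binomial proportions with alpha of 0.05" (12.2; stated for the complications endpoint and taken here to apply to sensor failure too). For sensor failure, 663 subjects give more than 90% power for "a difference as small as 3.5% from the null proportion rate of 0.90", that is, 0.90 against 0.935.

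**Input not in the plan.** m, the share of all sensor failures by 24 months that are never detected and are counted as failure-free. It is assumed below.

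**Step 1: reproduce the plan's figure.** The exact two-sided 95% lower limit must exceed 0.90.
- With 612 of 663 failure-free (51 failures, 92.3%), the lower limit is 0.9001: pass.
- With 611 failure-free (52 failures), it is 0.8984: fail.
- The rule is therefore to pass at 51 or fewer failures.
- Power at true freedom 0.935 is P(X ≤ 51) with X ~ Binomial(663, 0.065) = 90.5%. The stated 663 reproduces.
- At true freedom of exactly 0.90, P(X ≤ 51) with X ~ Binomial(663, 0.10) = 2.5%, as intended.

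**Step 2: let a share m of failures go unseen.** The observed failure probability becomes f × (1 − m), where f is the true failure probability, and the chance of passing is P(X ≤ 51) with X ~ Binomial(663, f(1 − m)).

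| Share of failures missed, m | Observed failure probability (f = 0.10) | Chance of passing, true freedom 90% | Chance of passing, true freedom 88% (f = 0.12) |
|---|---|---|---|
| 0% | 0.100 | 2.5% | 0.02% |
| 5% | 0.095 | 6.1% | 0.1% |
| 10% | 0.090 | 13.3% | 0.4% |
| 20% | 0.080 | 42.0% | 5.1% |
| 30% | 0.070 | 78.3% | 28.3% |

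The test is sensitive because few failures separate the null from a pass. At 90% freedom the expected count is 663 × 0.10 = 66.3, and 51 is enough to pass.

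**Step 3: relate m to non-use.** m is not the share u of patients who have stopped reading. A non-user's failure is missed only if it comes after the last reading. If stopping and failure times are independent and both uniform over 24 months, and non-users fail as often as users (all assumptions), half of the failures in non-users are missed and m = u/2. Then u = 10% gives m = 5% (6.1% chance of passing), u = 20% gives m = 10% (13.3%), and u = 40% gives m = 20% (42.0%).

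**The case against.** The best defence is that routine use covers the gap. Patients are asked to read daily or as directed, and are reminded at each visit (8.3). Someone whose sensor fails during use gets no successful-reading notice (8.4) and is told to call technical support about problems (16.3). Adverse events are assessed at every follow-up visit, and sensor malfunction and failure to transmit are both listed as anticipated device effects (11.6.2). Persistent non-users may also be withdrawn for noncompliance (8.6). All of this stands, and it makes a silent failure less likely. None of it obliges anyone to attempt a reading in a patient who has stopped.

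Three stronger readings are tempting and are not supported:
- A reader might infer that patients without recent readings are counted as successes. That is the likely default, since no event would be on record, but the plan does not say so. They could be failure-free, censored or excluded, and exclusion would not necessarily favour the device.
- A reader might infer that no visit at all requires a reading. The implant visit does (8.2).
- A reader might equate the share of non-users with the share of failures missed. Step 3 shows that this overstates the effect: at u = 20%, the chance of passing is 13% if half of their failures are missed, against 42% if all are.

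**Conclusion.** The gap is real. A primary safety endpoint depends on an attempted reading that no follow-up or exit visit requires, and the status of a sensor with no recent reading is undefined. Failures after the last home reading can go unrecorded and, if counted as failure-free, favour the device. Leaving the classification open also means it could be settled after results are known.

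The size is unknown, because the documents give neither the share of patients who stop reading nor the share of failures that would be missed. With 663 subjects and true freedom of 90%, the chance of wrongly passing rises from 2.5% to 6%, 13% and 42% when 5%, 10% and 20% of all failures are missed. These figures show how sensitive the test is and do not forecast the result. They assume the exact interval and that missed failures count as failure-free. At a true freedom of 88%, a false pass stays unlikely (about 5%) even with 20% missed.

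**What to change.** 1. **Visits (8.3, 8.6, Appendix B).** Replace investigator discretion with one required sensor reading attempt at Month 24 and at exit, where possible. A failed attempt triggers the troubleshooting in 9.1.2. This can reach only subjects who have not completed Month 24. Version C is dated February 2018, and on the anticipated timeline in Appendix A about 267 subjects (cumulative enrolment for February 2016) would already be at that point.

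2. **Analysis (12.6.1, 13.9.1).** Keep every documented sensor failure as an event, and state in advance how the primary analysis classifies implanted subjects with unknown sensor status. Using the reading dates already in the database, identify subjects with no documented failure and no successful reading at or after 24 months minus 30 days. Add two sensitivity analyses:
   - Censor these subjects at their last successful reading (Kaplan-Meier). Documented failures must not be censored by this rule.
   - Count them as failures. This is needed because stopping may itself result from a sensor problem, in which case censoring is informative. Report it for subjects still in follow-up at Month 24, apart from those who died or left earlier and so lack a late reading for another reason.

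Both belong in sensitivity analyses because the study was sized on an exact binomial test, which does not accommodate censoring. The second is a bound and should not be a pass/fail rule: with 663 subjects, 52 failures and unknowns combined (52/663 = 7.8%) would already miss the criterion.

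**Cost.** A short non-invasive reading at a visit already scheduled, a little more analysis, and a wider interval in the censored version. As a pessimistic guide, dropping 20% of the 663 outright leaves 530 and reduces exact power at 93.5% freedom from 90.5% to about 81%; dropping 40% leaves 398 and about 64%. Censoring loses less than dropping. The primary sample size does not change.

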8.4. Subject Home PA Pressure Readings

Prior to hospital discharge, subjects will be instructed on how to take their own pulmonary artery pressure measurements, utilizing the CardioMEMS HF System. Subjects will provide returned demonstration on: setting up the unit, connecting the system to a phone line, proper positioning for obtaining the optimum sensor signal, taking and transmitting the daily pressure measurements. The unit will transmit the data to a database using the system's modem.

The home measurements will be taken while the subject is lying down (supine) in bed positioned on a padded, flat antenna. It is recommended that subjects obtain home measurements in a supine position however, if the subject is unable to lie flat, measurements can be obtained in a sitting or reclined position. It is important the anatomical position is consistent for every measurement.

The home electronics system is small enough for placement on a bedside table. The unit will provide audio and visual prompts for the subject to guide them through signal acquisition. Once the subject is positioned and a signal is acquired, the subject will be notified of the successful reading and the data is automatically transmitted to a remote database. St. Jude Medical will provide instructions for use and a help line will be available. Please refer to subject's Patient System Guide for more detailed information.

8.5. PA Pressure Readings in the Hospital

If a subject is hospitalized, seen in the emergency room (ER) or has a clinic visit, the CardioMEMS HF System may be used to obtain pulmonary artery pressure measurements at the investigators discretion. Following sensor implant, subsequent RHC procedures or pulmonary artery catheter insertions must be performed under fluoroscopic guidance.

Resetting of the sensor baseline will be performed as deemed necessary by Sponsor. Baseline resetting may require an echocardiogram or a RHC procedure.

Following the sensor implant, should a RHC procedure or PA catheter evaluation be clinically warranted, comparative pulmonary artery pressures utilizing the CardioMEMS HF System should also be obtained utilizing the hospital electronics unit.

8.6. Criteria for Withdrawal

Subjects may be withdrawn from the study for any of the following reasons:

1. Subject withdraws his/her consent
2. Investigator determines that other treatment is warranted to protect the health and safety of the subject

This confidential document is the property of Abbott and shall not be reproduced, distributed, disclosed or used without the express written consent of Abbott

Clinical Investigation Plan

3. Investigator determines that the subject is noncompliant with study related procedures
4. Subject is lost to follow-up: site must document attempts made to contact the subject for an early discontinuation visit (e.g., 2 – 3 phone calls, followed by 1 certified letter, documentation of repetitive missed study visits, etc.)

The Investigator will notify the Sponsor and document on the appropriate case report form (CRF) the reason/circumstances for early discontinuation. All subjects who withdraw from the study should have the following study exit procedures performed if possible:

- Updated medical and surgical history
- Assessment of AEs that occurred since the last visit
- Abbreviated physical examination (only significant changes since Enrollment) including vital signs (temperature, heart rate, respiratory rate, blood pressure), and weight
- Assessment of NYHA functional class
- Kansas City Cardiomyopathy Questionnaire(KCCQ-12)
- Brief Illness Perception Questionnaire
- Cardiac Health Security Survey
- Heart failure Medication Review
- PA pressures may be obtained at the Investigator's discretion

All reasonable efforts should be made to retain subjects in the clinical trial until its completion. If a patient moves from the geographic area of their investigator, St. Jude Medical will attempt to place the patient with another investigator.

